| Study Duration                         | The total study duration is approximately 52 weeks (from the first dose of study drug in this study), including a Treatment Period of 48 weeks and a Safety Follow-up Visit 4 weeks after the last dose of study drug.                                                                                                                                                                                                                  |
| Study Design                           | This is a Phase 3b, multicenter, open-label study for subjects who complete a parent study (VX19-445-117 or VX20-445-126) and meet eligibility criteria. A schematic of the study design is shown in Figure 2-1.                                                                                                                                                                                                                        |

**Figure 2-1** VX20-445-121 Study Design

ELX: elexacaftor; IVA: ivacaftor; TEZ: tezacaftor

Note: Figure is not drawn to scale.

Subjects will receive a dose of ELX 200 mg once daily (qd)/TEZ 100 mg qd/IVA 150 mg every 12 hours (q12h).

For treatment continuity in regions where ELX/TEZ/IVA is not commercially available, an option to return to this study will be offered to subjects who depart this study to enroll in another Vertex study of investigational CFTR modulators (hereafter referred to as “another qualified Vertex study”) based on the following:

- Subjects have received open-label ELX/TEZ/IVA during the other study’s Run-in Period but have not received study drug in the Treatment Period of the other study, and
- Meet all eligibility criteria for this study at their Returning Visit

Subjects who resume participation in this study will resume treatment with study drug after completion of a Returning Visit. Resumption of participation in this study following departure to another qualified Vertex study will be permitted only once.

**Assessments** Safety: AEs, clinical laboratory assessments, ECGs, vital signs and pulse oximetry, physical examinations (PES), and ophthalmologic examinations

**Statistical Analyses** The safety analysis will be conducted for subjects who have received at least 1 dose of study drug in this open-label study. The safety analysis will be descriptive only.

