| Study drug count                   | X                                                                        |                                                          | X                                   | X                          | X                                             | X                                                                                       |                                                                                                                                                                                                                                      |
| Study drug dosing                  | Day 1 through evening before Week 48 Visit                               |                                                          |                                     |                            |                                               |                                                                                         | Subjects on study drug interruption from a parent study or another qualified Vertex study may NOT begin dosing until they meet the resumption criteria in Section 9.8. Refer to Section 9.6.1 for study drug administration details. |
| Adverse events                     | Continuous from signing of ICF through completion of study participation |                                                          |                                     |                            |                                               |                                                                                         | Section 11.2.1                                                                                                                                                                                                                       |
| Medications review                 | Continuous from signing of ICF through completion of study participation |                                                          |                                     |                            |                                               |                                                                                         | Section 9.5                                                                                                                                                                                                                          |

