### 9.3.2 Study Drug Dose and Duration

To evaluate safety and tolerability the study drug doses evaluated are the same as the doses evaluated in a parent study.

The overall treatment duration will be 48 weeks, which is considered sufficient for evaluating the safety of treatment with ELX/TEZ/IVA.

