### **9.2.5 Study Drug Exposure**

Study drug exposure will be summarized based on the Safety Set. Duration of study drug exposure (in days) will be calculated as [last dose date – first dose date + 1 day] within the TE period, regardless of any interruption in dosing between the first and the last dose. For subjects who enroll in another qualified Vertex study and resume participation in this study, time spent in the other study will be excluded.

Study drug exposure (in weeks) will be summarized descriptively by the number of subjects (n), mean, SD, median, min, and max. It will also be summarized by interval, using counts and percentages.

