### **9.2.6 Study Drug Compliance**

Study drug compliance will be summarized based on the Safety Set, and will be calculated as:  $100 \times [1 - (\text{total number of days of study drug interruption in this open-label study}) / (\text{duration of study drug exposure in days in his open-label study})]$ . A study drug interruption on a given day is defined as an interruption of any study drug on that day. For subjects who enroll in another qualified Vertex study and resume participation in this study, time spent in the other study will be excluded.

Percentage of study drug compliance will be summarized based on the Safety Set. Percentage of study drug compliance will be summarized descriptively by the number of subjects (n), mean,

SD, median, min, and max. It will also be summarized in categories: <80% and  $\geq 80\%$  using frequency tables.

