 For safety assessments, Safety Follow-up analysis visit will be based on nominal Safety Follow-up visit. If a subject does not have a nominal Safety Follow-up visit but has an ETT visit with study day >351, then the ETT visit will be mapped into Safety Follow-up analysis visit for the corresponding part.

 Baseline coagulation applies to subjects from parent study 445-117 only; baseline coagulation will be missing for subjects from parent study 445-126.

Derived Variables for each part:

1. Age (in years) at first dose date and post-baseline visit (for demographics, listing and the calculation of [percent] predicted spirometry variables):

Obtain the age at informed consent in “yy, mm” format (e.g., 24 years, 6 months) from the Vital Signs (VS) page at the Day 1 Visit and add 0.5 month to convert to days.

Obtain the informed consent date.

Then age (in years) at first dose or post-baseline visit = [(first dose date or post-baseline visit date – informed consent date) in days + age at informed consent (in days)]/365.25.

2. Missing first dose date or last dose date

If the first dose date is missing, use Day 1 visit date.

If the last dose date of study drug is not available and there is no data to indicate that the subject discontinued treatment, the data cutoff date will be used instead.

If the subject discontinued treatment and the last dose date is missing or partial date is reported, the last dose date will be imputed based on, in descending order priority, the Early Treatment Termination (ETT) visit date, last visit date before the Safety Follow-up, or the last study drug administration date from EX SDTM domain, as appropriate. The imputation algorithm will ensure the imputed last dose date does not exceed the data cutoff date.

3. Electrocardiogram:

Baseline is defined in Section 8.1. If multiple ECG measurements are obtained on the same calendar day during the TE period,

- o For summary purpose, the average value will be used as the ECG on that day;
- o For threshold analysis purpose, all ECG values will be used

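### SAP Appendix A sets a missing last dose date to the data cutoff when no discontinuation is recorded; in this fixed 48-week study that is too late for any completer it reaches, though the effect is small and may be nil

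*SAP*

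**What the plan says.** SAP Appendix A, derived variables, item 2, has two branches for a missing last dose date.

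- **No recorded discontinuation.** The condition is "If the last dose date of study drug is not available and there is no data to indicate that the subject discontinued treatment", and then "the data cutoff date will be used instead". The SAP does not define that cutoff.
- **Recorded discontinuation.** The date comes from the ETT visit first, then "last visit date before the Safety Follow-up, or the last study drug administration date from EX SDTM domain, as appropriate". A closing sentence keeps the imputed date from passing the cutoff. That does not help in the first branch, where the imputed date is the cutoff.

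The Protocol fixes the end of dosing. Section 9.3.2 states "The overall treatment duration will be 48 weeks", and Table 3-1 gives study drug dosing as "Day 1 through evening before Week 48 Visit". Interim analysis is marked not applicable in Protocol 12.4 and SAP 10.1.

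The last dose date feeds three derivations:

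- SAP 9.2.5 computes exposure as "last dose date – first dose date + 1 day] within the TE period" (the bracket opens just before these words).
- SAP 9.2.6 divides interruption days by that exposure to get compliance. "It will also be summarized in categories: <80% and" at least 80%.
- SAP 9.1 ends the TE Period at the earlier of 28 days past the last dose and completion of participation. Protocol 9.1.5 makes completion the Safety Follow-up Visit, unless the ETT, Departing or Week 48 Visit stands in for it.

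**The concern.** A data cutoff is a reasonable stand-in when a snapshot is taken while subjects are still dosing. No such snapshot is planned here. By the final analysis nobody should be on study drug, so the first branch can reach only a completer whose date is missing, or a subject with no record of having stopped. For a completer, Table 3-1 places the last dose on the evening before the Week 48 Visit, so the cutoff must be later than the true date. Better sources (the last visit before Safety Follow-up, the EX record) are already in the same item, but only for subjects who discontinued.

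The wording looks carried over from a plan with an interim cut. Appendix C also limits partial AE end dates by an interim cutoff that this study does not have.

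The possible errors all run one way: longer exposure, higher compliance, a later end to the TE Period. Safety is the study's only objective, and these quantities underlie its reporting.

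**Working it through.** 1. **Timeline.** 48 + 4 = 52 weeks, which reproduces "The total study duration is approximately 52 weeks" in the Protocol synopsis. The Week 48 target day is 48 × 7 + 1 = 337, as in SAP Table 12-1. With the last dose on the evening before, Day 336, true exposure is 336 − 1 + 1 = 336 days.

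2. **The SAP's limit.** Let C be the cutoff day and E the day participation is completed, with C on or after E. With the last dose set to C, the TE Period ends at min(C + 28, E) = E. Exposure counted within the TE Period is then E days.

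3. **Exposure for a completer, Week 48 Visit on target.** The Safety Follow-up window is 28 (± 7) days after the last dose (Protocol 9.1.2).

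| Completion of participation | E = exposure counted (days) | Excess (days) | Excess / 336 |
|---|---|---|---|
| Week 48 Visit replaces Safety Follow-up | 337 | 1 | 0.3% |
| Safety Follow-up 21 days after last dose | 357 | 21 | 6.2% |
| Safety Follow-up 28 days after last dose | 364 | 28 | 8.3% |
| Safety Follow-up 35 days after last dose | 371 | 35 | 10.4% |

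   If the Week 48 Visit moves within its ± 5 days, true exposure is 331 to 341 days. The 21- to 35-day excess does not change, and as a percentage it runs from 6.2% to 10.6%.

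4. **End of the TE Period.** With the true last dose it is min(336 + 28, E) = min(364, E); with the imputed one it is E. The difference is max(0, E − 364), which is 0 for E = 337, 357 or 364 and 7 days for E = 371. The end moves only when Safety Follow-up falls 29 to 35 days after the last dose, and then by 1 to 7 days.

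5. **Compliance**, 100 × (1 − interruption days / exposure), taking the added days as not recorded as interruptions. With an assumed 70 interruption days: 100 × (1 − 70/336) = 79.2%, against 100 × (1 − 70/364) = 80.8%. With no interruptions both are 100%. For a 28-day excess, the 80% line is crossed only if interruption days exceed 0.2 × 336 = 67.2 and do not exceed 0.2 × 364 = 72.8, that is, 68 to 72 days. For a 1-day excess the upper limit is 0.2 × 337 = 67.4, and no whole number of days qualifies.

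6. **Study-level effect.** The number affected, k, is not given. At 28 days each among 160 subjects, mean exposure shifts by 28k/160 days: 0 for k = 0, 0.18 for k = 1, and 0.88 for k = 5 (0.26% of 336).

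**The case against.** The strongest reply is that the rule may never fire. Study drug is counted at Week 48 and at Safety Follow-up (Protocol Table 3-1). Completion or discontinuation of treatment is recorded for disposition (SAP 9.2.1), and loss to follow-up has explicit criteria (Protocol 9.1.4), so most subjects without a clean end of treatment should fall under the discontinued branch. The analysis is also descriptive, with no testing (SAP 9.3). All of this stands, and it is why the number affected may be zero. It does not make the rule right. SAP 9.2.1 keeps completed and discontinued treatment apart, so a completer with a missing date falls to the cutoff.

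A reader might infer four stronger claims that the documents do not support.

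- **Exposure inflated by months.** Protocol 12.3.2.4 defines exposure without the TE limit. On that wording alone, a cutoff 52 weeks after a Day 364 Safety Follow-up would give 364 + 52 × 7 = 728 days. SAP 9.2.5, which governs the calculation, limits exposure to the TE Period, so counting stops at completion of participation.
- **A 28-day error for most affected completers.** Under Protocol 9.1.2 the Week 48 Visit replaces Safety Follow-up for subjects who move within 28 days to a commercial or managed-access Vertex CFTR modulator or to another qualified study. The proportions are not given, and for these subjects the excess is about 1 day.
- **Late events routinely becoming TEAEs.** This can happen only when Safety Follow-up falls 29 to 35 days after the last dose.
- **Compliance generally crossing 80%.** This needs an interruption total within the narrow band in step 5.

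**Conclusion.** The point holds as a minor defect. As written, the rule gives too late a date for any completer it reaches, by an amount that depends on which visit closes participation: about 1 day, or 21 to 35 days. The effects on compliance and on the TE Period are conditional and small. Unless far more subjects are affected than seems likely, study-level exposure changes by less than a day on average.

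This rests on reading the SAP's TE-period wording as a cap on the last dose date, on a cutoff no earlier than the subject's completion of participation, and on a Week 48 Visit on target. The 70 interruption days and the values of k are illustrations, not figures from the documents. For a subject with neither a Week 48 Visit nor a recorded discontinuation, the cap is that subject's own completion date (date of last contact if lost to follow-up), and the documents do not allow the error to be sized.

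**What to change.** In SAP Appendix A, item 2, first branch, replace the data cutoff date for the final analysis with sources the item already names, in this order:

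1. the last study drug administration date in EX, if available;
2. otherwise the date of the last visit before Safety Follow-up, and for subjects who completed treatment no later than the day before the Week 48 Visit.

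Keep the cutoff date only for a data cut taken while subjects are still dosing, and define it there.

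EX comes first so that a completer whose record shows an earlier last administration is not moved forward to Week 48. The Week 48 ceiling is limited to completers because it has no meaning for a subject without that visit. For a completer on target with no EX date, the result is Day 336, the planned exposure; without the ceiling it would be Day 337.

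The cost is a line or two of SAP text and a small change to the last-dose derivation before database lock. No new data are needed. Reported exposure becomes slightly shorter for any affected subject.

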## Appendix B: Imputation Rules for Missing Prior/Concomitant Medication Dates

Imputation rules for missing or partial medication start/stop dates are defined below:

1. Missing or partial medication start date:
  - a. If only DAY is missing, use the first day of the month.
  - b. If DAY and Month are both missing, use the first day of the year.
  - c. If DAY, Month and Year are all missing, use a date before the first dose date (to impute in practical, use the parent study informed consent date).
2. Missing or partial medication stop date:
  - a. If only DAY is missing, use the last day of the month.
  - b. If DAY and Month are both missing, use the last day of the year.
  - c. If DAY, Month and year are all missing, assign ‘continuing’ status to stop date (to impute in practical, use the end of study date).

In summary, the prior, concomitant, or post categorization of a medication is described below.

**Table 12-2 Prior, Concomitant, and Post Categorization of a Medication**

Medication Start Date	Medication Stop Date		
	< First Dose Date of Study Drug	≥ First Dose Date and ≤ End Date of TE Period	> End Date of TE Period
< First dose date of study drug	P	PC	PCA
≥ First dose date and ≤ End date of TE period	-	C	CA
> End date of TE period	-	-	A

P: Prior; C: Concomitant; A: Post

Same imputation rule will be implemented for missing and/or partial dates of non-pharmacological treatment/procedure.

## Appendix C: Imputation Rules for Missing AE dates

Imputation rules for missing or partial AE start date are defined below. If the imputed AE start date is before the informed consent date for the OLS, the AE start date will be imputed using the informed consent date. Ongoing events from the parent study will follow the imputation rule described in the SAP for parent study.

- **If only Day of AE start date is missing:**

- If the full (or partial) AE end date is NOT before the first dose date of the OLS or AE end date is missing, then
  - if AE start Year and Month are equal to the Year and Month of the first dose date of OLS, then impute the AE start Day as the Day of the first dose date of OLS;
  - else impute the AE start day as 1.
- else impute the AE start day as 1.

- **If Day and Month of AE start date are missing:**

- If the full (or partial) AE end date is NOT before the first dose date of the OLS or AE end date is missing, then
  - if AE start Year is equal to the Year of the first dose date of OLS, then impute the AE start Month and Day as the Month and Day of the first dose date of OLS;
  - else impute the AE start Month as January and Day as 1.
- else impute the AE start Month as January and Day as 1.

- **If Year of AE start date is missing:**

If the Year of AE start date is missing or AE start date is completely missing then query site.

- If the full (or partial) AE end date is NOT before the first dose date of the Treatment Period or AE end date is missing, then impute the AE start date as the first dose date of the OLS.
- else impute the AE start date as the informed consent date.

Compare the imputed AE start date with TE period to determine whether the AE is pre-treatment AE, TEAE or post-treatment AE.

Imputation rules for partial AE end date are defined below:

If partial end date, then impute as min (the last day of the month, data cut-off for IA, end of study) if day is missing, or min (Dec, data cut-off for IA, end of study) if month is missing.

## Appendix D: Adverse Events of Special Interest

Table 12-7 MedDRA Preferred Terms for Event of Special Interest	
Adverse event of special interest	MedDRA preferred terms
Elevated transaminases	Alanine aminotransferase abnormal, Alanine aminotransferase increased, Aspartate aminotransferase abnormal, Aspartate aminotransferase increased, Transaminases abnormal, Transaminases increased, Liver function test abnormal, Liver function test increased, Hypertransaminasaemia, Hepatic enzyme abnormal, Hepatic enzyme increased
Rash	Rash, Rash erythematous, Rash macular, Rash maculo-papular, Rash maculovesicular, Rash vesicular, Rash pruritic, Rash follicular, Rash pustular, Nodular rash, Drug eruption, Fixed eruption, Urticaria, Urticaria papular, Urticaria vesiculosa, Urticarial dermatitis, Rash morbilliform, Rash papular, Rash papulosquamous, Rash rubelliform, Rash scarlatiniform , Drug hypersensitivity, Type IV hypersensitivity reaction, Dermatitis, Dermatitis atopic, Epidermolysis, Skin toxicity, Dermatitis allergic, Dermatitis exfoliative, Dermatitis exfoliative generalised, Erythema multiforme, Exfoliative rash, Mucocutaneous rash, Acute generalised exanthematous pustulosis, Cutaneous vasculitis, Urticarial vasculitis, Dermatitis bullous, Drug reaction with eosinophilia and systemic symptoms, Epidermal necrosis, Oculomucocutaneous syndrome, Skin exfoliation, Skin necrosis, Stevens-Johnson syndrome, Toxic epidermal necrolysis, Toxic skin eruption, Perioral dermatitis, Vasculitic rash, Immune-mediated dermatitis, Penile rash, SJS-TEN overlap, Erythrodermic atopic dermatitis, Scrotal dermatitis, Anal Rash, Generalised bullous fixed drug eruption

Note: The preferred terms listed in the table is based on the MedDRA version applicable at the time of finalization of the SAP. If the MedDRA version is upgraded at the time of the final analysis, the corresponding preferred terms based on the upgraded version will be used in the analysis of adverse events of special interest.

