#### **9.8.1 Liver Function Tests**

The central laboratory will notify the medical monitor of alanine transaminase (ALT) or aspartate transaminase (AST) >3 × upper limit of normal (ULN) and total bilirubin >2 × ULN that are derived from centrally submitted samples.

Subjects with new treatment-emergent (TE) ALT or AST elevations of >3 × ULN, with or without total bilirubin >2 × ULN, must be followed closely, including confirmatory testing performed by the central laboratory within 48 to 72 hours of the initial finding and subsequent close monitoring of ALT, AST, and bilirubin levels, as clinically indicated.

If a subject cannot return to the site for confirmatory testing, a local laboratory may be used. Local laboratory results must be reported immediately to the medical monitor, and the subject must have the tests repeated and sent to the central laboratory as soon as possible (ideally within 48 to 72 hours).

Study drug administration **must be interrupted** immediately (prior to confirmatory testing) if any of the following criteria are met:

- ALT or AST  $>8 \times$  ULN
- ALT or AST  $>5 \times$  ULN for more than 2 weeks
- ALT or AST  $>3 \times$  ULN, in association with total bilirubin  $>2 \times$  ULN and/or clinical jaundice

A thorough investigation of potential causes should be conducted, and the subject should be followed closely for clinical progression.

Subjects who enroll in this study on a drug interruption because of transaminase elevations in a parent study may NOT receive the first dose of study drug until transaminases return to baseline values or  $\leq 2 \times$  ULN, whichever is higher.

Study drug administration **must be discontinued** if the following criteria are met:

- Subsequent ALT or AST values confirm the initial elevation that satisfied the interruption rule (above), and no convincing alternative etiology (e.g., acetaminophen use, viral hepatitis, alcohol ingestion) is identified, regardless of whether transaminase levels have improved

All subjects in whom treatment is discontinued for elevated transaminases (and bilirubin, as applicable) should have these levels monitored closely until levels normalize or return to baseline.

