##### **13.1.1.2 Clinically Significant Assessments**

Study assessments including laboratory tests, ECGs, PEs, and vital signs will be assessed and those deemed to have clinically significant worsening from baseline will be documented as an AE. When possible, a clinical diagnosis for the study assessment will be provided, rather than the abnormal test result alone (e.g., urinary tract infection, anemia). In the absence of a diagnosis, the abnormal study assessment itself will be listed as the AE (e.g., bacteria in urine or decreased hemoglobin).

An abnormal study assessment is considered clinically significant if the subject has 1 or more of the following:

- Concomitant signs or symptoms related to the abnormal study assessment
- Further diagnostic testing or medical/surgical intervention
- A change in the dose of study drug or discontinuation from the study

Repeat testing to determine whether the result is abnormal, in the absence of any of the above criteria, does not necessarily meet clinically significant criteria. The determination of whether the study assessment results are clinically significant will be made by the investigator.

A laboratory value that is Grade 4 will not automatically be an SAE. A Grade 4 laboratory value will be an SAE if the subject's clinical status indicates a life-threatening AE.

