### **13.1.1.3 Documentation of Adverse Events**

All AEs will be collected from the time the ICF is signed until the following times:

- For subjects who do not enroll: until time of screen failure (e.g., screen failure, withdrawal of consent)
- For enrolled subjects who have a Safety Follow-up Visit: through the Safety Follow-up Visit
- For enrolled subjects who do not have a Safety Follow-up Visit, the earliest of
  - 28 days after the last dose of study drug, or
  - the ETT Visit, if that visit is 3 weeks or later following the last dose of study drug (see Section 9.1.3)
- For subjects who depart this study to enroll in another qualified Vertex study: through the time of enrollment in another qualified Vertex study
- For subjects who depart this study to enroll in another qualified Vertex study and resume participation in this study, AEs will be collected from the time of the Returning Visit until the subject completes study participation in this study. AEs that fully occur (start and end) in the other qualified Vertex study will be recorded as medical history; AEs that started during participation in the other qualified Vertex study and are ongoing at the time of the Returning Visit in this study will be recorded as AEs in this study.

All subjects or the subjects' parents or legal guardians, as appropriate, will be queried, using nonleading questions, about the occurrence of AEs at each study visit. When possible, a constellation of signs and/or symptoms will be identified as 1 overall event or diagnosis. All AEs for enrolled subjects will be recorded in the CRF and source document. AEs for subjects who are screened but not subsequently enrolled will be recorded only in the subject's source documents.

The following data will be documented for each AE:

- Description of the event
- Classification of "serious" or "nonserious"
- Date of first occurrence and date of resolution (if applicable)
- Severity
- Causal relationship to study drug(s)
- Action taken
- Outcome
- Concomitant medication or other treatment given

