### **9.3.1.1 Adverse Events of Special Interest**

For this study, elevated transaminases events and rash events, as determined by MedDRA Preferred Terms in [Appendix D](#), are considered as adverse events of special interest. The corresponding AE data will be summarized in terms of frequency counts.

For treatment-emergent elevated transaminases events and rash events, the following categories will be summarized:

- Subjects with events
- Subjects with events by maximum severity
- Subjects with events leading to treatment discontinuation
- Subjects with events leading to treatment interruption
- Subjects with serious events
- Subjects with study drug related serious events
- Subjects with events leading to death
- Duration of events
- Time-to-onset of first event (with the first dose date of ELX/TEZ/IVA in the open-label study as the reference while calculating time-to-onset)

In addition, for treatment-emergent rash events, the above categories will be summarized for the following subgroups:

- Sex (male, female)
- Female subjects with concomitant hormonal therapy (Yes, No)

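### The elevated-transaminases AESI is defined only by laboratory-finding terms, so an elevation recorded only as a hepatic diagnosis is not counted in the AESI summary

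*SAP*

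**What the plan says.** SAP Section 9.3.1.1 names two groups of events of special interest, "elevated transaminases events and rash events, as determined by MedDRA Preferred Terms in" Appendix D. No laboratory criterion or medical review is given as another way in. For each group it plans counts of subjects with events, by maximum severity, leading to discontinuation or interruption, serious, related serious and fatal, together with duration and time to first onset.

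The elevated-transaminases row of Appendix D holds abnormal or increased terms for ALT, AST, transaminases, liver function test and hepatic enzyme, plus one synonym. It closes with "Hypertransaminasaemia, Hepatic enzyme abnormal, Hepatic enzyme increased". The rash row of the same table contains simple findings and also severe diagnoses, such as "Stevens-Johnson syndrome, Toxic epidermal necrolysis".

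On recording, Protocol Section 13.1.1.2 says: "When possible, a clinical diagnosis for the study assessment will be provided, rather than the abnormal test result alone". It continues: "In the absence of a diagnosis, the abnormal study assessment itself will be listed as the AE". Section 13.1.1.3 adds: "When possible, a constellation of signs and/or symptoms will be identified as 1 overall event or diagnosis".

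**The concern.** The reporting rule and the term list pull in different directions. The protocol prefers a diagnosis where one can be made; the AESI list recognises only the test finding. An investigator who follows the protocol and enters one hepatic diagnosis, without a separate entry for the enzyme rise, produces an event that matches no listed term.

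Safety and tolerability is the study's only objective, and the AESI table is where a reader will look for one pooled hepatic count with severity, seriousness, action taken, duration and onset. If a case is coded by diagnosis, a zero in the serious or discontinuation line could mean that no event occurred or that the event carried an unlisted term. The table does not tell the reader which.

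**Working it through.** The plan states no figure on this point, so there is none to reproduce. The check is a count of terms, a trace of how an event flows through the outputs, and an illustration of scale.

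**1. Term count (SAP Appendix D).** The elevated-transaminases row has 11 terms. Ten end in *abnormal* or *increased*; the eleventh is hypertransaminasaemia. A search of the row for hepatit-, injury, failure, jaundice, cholesta-, bilirubin, necrosis and hepatotox- finds nothing. The rash row has 54 terms and includes severe diagnoses.

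**2. Trace of one elevation under each way of recording it.**

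| Recorded as | Matches a listed term? | AESI summary | Threshold tables | General TEAE tables and listings |
|---|---|---|---|---|
| Test finding only | Yes, if coded to one of the 11 | Counted | Counted if the value qualifies | Under the test term |
| Diagnosis and test finding | Yes, through the test finding | Counted (the finding, not the diagnosis) | Counted if the value qualifies | Under both terms |
| Diagnosis only | No | Not counted in any category | Counted if the value qualifies | Under the diagnosis |

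Only the third line loses anything. Sections 13.1.1.2 and 13.1.1.3 of the protocol permit it and, when a diagnosis is possible, lean towards it.

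**3. What the other outputs supply.** SAP Section 9.3.2 with Tables 12-3 and 12-4 counts subjects by ALT and AST band, by ALT or AST >3×ULN with total bilirubin >2×ULN, and by >3×, >5× and >8×ULN, whatever the AE coding. These tables carry no seriousness, action taken, duration or onset. SAP Section 9.3.1 gives serious, related serious, Grade 3/4/5, discontinuation, interruption and fatal tables by SOC and Preferred Term, with subject listings. These carry seriousness and action taken, but spread over separate terms and without a pooled hepatic count, duration or time to onset.

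**4. Scale.** Expected enrolment is N = 160 (SAP Section 7.2).

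- One subject: 1/160 = 0.625%. For scale only, since the SAP plans no intervals, the exact 95% interval for 1/160 is about 0.02% to 3.4%. For 0/160 the upper limit is 1 − 0.025^(1/160) = 2.3%.
- Illustration: let p be the true proportion of subjects with an elevation event and f the share of those recorded only as a diagnosis. **Neither is in the documents; both are assumed.** The expected AESI count is N·p·(1 − f). The chance that at least one subject is missed is 1 − (1 − p·f)^N.

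| p | True expected count | Counted, f = 10% | Counted, f = 50% | P(≥1 missed), f = 10% | P(≥1 missed), f = 50% |
|---|---|---|---|---|---|
| 2% | 3.2 | 2.9 | 1.6 | 0.27 | 0.80 |
| 5% | 8.0 | 7.2 | 4.0 | 0.55 | 0.98 |
| 10% | 16.0 | 14.4 | 8.0 | 0.80 | about 1.00 |

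The range is too wide to serve as an estimate. It shows only that a missed subject is plausible unless both p and f are small.

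**The case against.** The best defence is that the row does what its name says. It is called elevated transaminases, not liver injury, and a list of abnormal or raised enzyme and liver-test terms fits that name. Hepatitis or jaundice is not itself an enzyme elevation, and a broad hepatic query could admit events with no transaminase rise. This stands as a reason not to redefine the row. It does not remove the gap, because a real transaminase elevation can still be missed through the way it was written down. The row also already reaches past transaminases to liver function test and hepatic enzyme terms. The contrast with the rash row helps only in part, since most of the severe diagnoses there are themselves skin eruptions.

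The second defence is that the reporting rule is conditional. It applies when possible, and preferring a diagnosis to the test result alone does not forbid recording both. This stands: the loss affects only events recorded solely as a diagnosis.

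The third is that nothing disappears from the safety analysis. In a descriptive study of about 160 subjects, a liver-injury case would appear by name in the tables and listings set out above, and its values in the threshold tables. This also stands.

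A reader might infer something stronger: that the list systematically removes the worst events, because these are the ones that acquire a diagnosis. Protocol Section 9.8.1 lends this some support, since for elevations that meet the interruption rule it says "A thorough investigation of potential causes should be conducted". But the same section ties discontinuation to a confirmed elevation with no convincing alternative cause. If no diagnosis follows, Section 13.1.1.2 makes the test result the AE, which is likely to code to a listed term. An investigator might still record drug-induced injury. The documents do not say how such events will be coded, so selection against the serious or discontinuation lines is not established.

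**Conclusion.** The gap is real and limited. As the SAP stands, a transaminase elevation recorded only as a hepatic diagnosis is counted in none of the Section 9.3.1.1 categories. This follows directly from term-only selection, 11 laboratory-finding terms and a conditional preference for diagnoses.

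The documents do not support saying that the most serious events drop out of the analysis, or that a reassuring zero is to be expected. The cases leave the AESI summary only. That they remain visible in the threshold tables assumes that the qualifying laboratory value is in the analysed data.

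The size cannot be estimated, because the documents give neither the event rate nor the share coded by diagnosis. At 160 subjects each affected subject moves a line by 0.625 percentage points, enough to turn one event into none. What is lost is the single pooled hepatic summary of seriousness, action taken, duration and onset, which no other planned table supplies.

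**What to change.** Leave the existing elevated-transaminases row unchanged, so that it can be compared with other summaries that use the same list. Add to Appendix D and Section 9.3.1.1 a supplementary row, *elevated transaminases or hepatic diagnosis*. Define it by the present 11 terms plus either a prespecified list of hepatic diagnosis terms (for example drug-induced liver injury, hepatotoxicity, hepatocellular injury, hepatitis, jaundice) or a standard drug-related hepatic disorders query. Report it in the same categories. A footnote to the narrow row should say that it covers events coded to laboratory-finding terms and point to Tables 12-3 and 12-4.

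The cost is a change to the SAP before database lock, documented as an amendment if the SAP is already approved, and one extra table row built from data already collected. Sites do nothing new. The downside is small: the added row is broader than transaminase elevation and is not directly comparable with summaries that use the narrow list, which is why both rows should be shown.
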